**Table 4 Initial Skeleton of Prior Guesses**

Dose (mg)	50	100	150	200	250	300	350	400	450	500	550	600	650	700	750	800
Prior guess of risk (%)	3	8	15	22	30	38	45	52	58	65	68	71	74	77	79	82

**Figure 7 Illustration of Model for the mCRM Design at Study Start (3 Patients Recruited at 100 mg without DLT).**

DLT=dose-limiting toxicity; mCRM=modified continual reassessment method with overdose control.

The prior model can be characterized as follows: based on the initial skeleton of prior guesses, the a priori MTD point estimate is 250 mg; this is the dose with the highest probability to have a DLT probability in the target interval of 25%–35%. After 3 patients were recruited at 100 mg without DLT, the recommended dose (after an update) is 250 mg. Furthermore, it is illustrative to consider various hypothetical trial realizations. If 3 patients are given the starting dose 100 mg and none of them develop a DLT, then the next mCRM dose recommendation is 250 mg. Afterwards the mCRM recommendations are 300 mg, 300 mg, 350 mg, 400 mg, 450 mg, 500 mg, 600 mg, 700 mg, and 800 mg if the next cohorts of 3 patients also have no DLT observed each time. The increase is a bit faster (not exceeding the maximum increments specified above) if more patients are enrolled into the cohorts. For example, if the cohorts are made with 6 patients rather than 3, all without DLTs, the dose recommended for the sequence of cohorts is 100 mg, 250 mg, 300 mg, 300 mg, 350 mg, 400 mg, 600 mg,

750 mg, and 800 mg. On the other hand, if DLTs are observed, the next recommended dose is (almost) equal to or lower than the current dose. Specifically, if in the first cohort at 100 mg with 3 patients when 1, 2, or 3 DLTs are observed, then the dose recommended for the second cohort is 100 mg, 50 mg, or 50 mg, respectively. If the first DLTs are observed in the second cohort of 3 patients at 250 mg and none in the first cohort of 100 mg, the dose for the third cohort is recommended as 250 mg, 200 mg, and 100 mg when 1, 2, or 3 DLTs are observed. A summary of the subsequent recommendation among same principle is provided in [Table 5](#).

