### **3.1.2.3 Dose-Toxicity Model with mCRM**

The dose escalation will employ a modified-Continual Reassessment Method with Overdose Control (mCRM) design in order to define MTD and/or the recommended dose. The design is based on the primary safety variable (the occurrence of a DLT). The MTD is defined as the dose that maximizes the probability of a DLT being in the targeted toxicity interval of 25%• 35%, subject to the probability of DLT being in the excessive toxicity interval of 35%• 100% being less than 35%. Patients within a cohort will be enrolled in a sequential manner in cohorts of at least 3 patients each, which, if required, can be expanded with additional patients. Each patient will be observed over 1 cycle (1 cycle lasts 28 days) of treatment for DLT assessment. The first patient in each cohort will be observed for safety for 1 week *after Cycle 1, Day 1* before enrolling additional patients in the cohort. After the last patient in each cohort has completed the 1-cycle DLT observation period, the Sponsor and investigators will evaluate the next dose recommended by the mCRM design and agree on the dose for the subsequent cohort. At each dose-escalation step, the dose can be escalated, de-escalated, or an additional cohort at the same dose-level can be enrolled.

The starting dose for idasanutlin will be 100 mg and the fixed dose for obinutuzumab will be 1000 mg. *The dose for rituximab starting from the bridging cohort for DLBCL patients will be 375 mg/m^2.* The dose-escalation is for the dose of idasanutlin. The maximum allowable increments for idasanutlin between dose levels will be as follows:

- 151% increase if the last idasanutlin dose is below or equal to 300 mg
- 33% of relative increase if the last idasanutlin dose is above 300 mg

The dose of idasanutlin will not be escalated above 800 mg. The selection of the next dose will be subject to clinical judgment and mandated safety constraints that limit the size of dose increments. Clinical judgment will always override mCRM recommendations in the dose-selection process.

The model-based dose escalation at each step will identify the next recommended dose level subject to the following criteria:

- The posterior probability of being within the excessive toxicity interval (above 35% DLT probability) is below 35%, and
- The posterior probability of being within the target toxicity interval (of 25%• 35% DLT probability) is maximized.

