Note: To fulfill the above statement, a loss function is being defined as per following:

- 0• 25 under dosing
- 25• 35 targeted toxicity
- 35• 60 excessive toxicity
- 60• 100 unacceptable toxicity

Where the “under dosing” and “excessive toxicity” are identically weighted to weight as much as the “unacceptable toxicity”; as such, the “targeted toxicity” will be maximized (i.e., Loss=[1,0,1,2]).

The dose-escalation will stop under the following circumstances:

- The maximum sample size of 40 patients has been reached, or
- At least a minimum of 9 patients across 3 cohorts has been accrued overall, at least 6 patients have been accrued at the MTD dose, and in addition the probability that the MTD dose lies within the target toxicity interval is above 40%.

The dose-toxicity relationship is described by a two-parameter logistic regression model:

$$\text{logit}[p(d_j^*)] = \log(\alpha) + \beta d_j^*$$

where  $p(d_j^*)$  denotes the probability to experience a DLT at dose  $d_j$  (mg), where  $d_j^* = \log(\frac{d_j}{d^R})$  is the transformed (i.e., standardized) dose using the reference dose,  $d^R = 300$ .

The following bivariate log normal prior distribution will be used for  $\alpha$  and  $\beta$  assuming no prior correlation between model parameters:

[figure not shown]
$$\begin{bmatrix} \log(\alpha) \\ \log(\beta) \end{bmatrix} \sim \mathcal{N} \left[ \begin{pmatrix} -1.237 \\ 0.460 \end{pmatrix}, \begin{pmatrix} 2.661 & 0 \\ 0 & 1.816 \end{pmatrix} \right]$$

A graphical representation based on this prior model is shown in [Figure 7](#) and has been constructed to match the skeleton of probability shown in [Table 4](#). This skeleton is based on a model built on an existing study (Study NP27872) and represents the most up-to-date relationship between dose and toxicities.

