**Table 5 Hypothetical Trial Realization (Cohort Size=3)**

Observation of First DLT at	Recommended Dose among the Number of DLT Effectively Observed		
	1 DLT	2 DLTs	3 DLTs
100 mg	100 mg	50 mg	50 mg
250 mg	250 mg	200 mg	100 mg
300 mg	300 mg	250 mg	250 mg
300 mg	300 mg	300 mg	300 mg
350 mg	350 mg	300 mg	300 mg
400 mg	400 mg	350 mg	350 mg
450 mg	450 mg	400 mg	400 mg
500 mg	500 mg	450 mg	450 mg
600 mg	650 mg	550 mg	500 mg
750 mg	800 mg	650 mg	600 mg

DLT=dose-limiting toxicity.

After each cohort of patients completes dosing, the posterior distribution of the model parameters of the logistic regression model will be updated with the observed DLT occurrence data and, hence, an estimate of the next dose, or declaration of MTD, will be derived. In addition relevant demographic, adverse event, laboratory, dose administration, and PK (if available) data will be reviewed. Then, subject to clinical judgment, a new cohort of patients will be dosed at the next recommended estimate of the MTD or the highest allowable dose based on the pre-specified over-dose constraints, whichever is lower. The design will continue as described, assigning patients to the MTD as estimated from all of the DLT data cumulatively, until one of the predefined stopping criteria is satisfied or the predetermined sample size of DLT-evaluable patients is reached, whichever comes first. *The above described mCRM algorithm will be first used for predicting the MTD in the combined FL/DLBCL dose-escalation cohorts where idasanutlin is given in combination with obinutuzumab. A similar mCRM will be then employed to support dose escalation in the DLBCL bridging cohorts where idasanutlin is given in combination with rituximab and in the FL bridging cohorts in which idasanutlin is given in combination with obinutuzumab using Regimen B, if applicable.*

With the end of the mCRM phase, a tentative MTD estimate is defined. Moreover, the recommended dose will be defined by taking into consideration all available data gathered so far.

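### The dose-selection loss function omits the 35% overdose limit it is said to enforce: six Table 5 doses breach the limit, and no rule says what happens when no dose meets it

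*Combined protocol and SAP*

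**What the plan says.** Section 3.1.2.3 gives two criteria for each model-based recommendation. The first is an overdose limit, in percentage terms: "The posterior probability of being within the excessive toxicity interval (above 35% DLT probability) is below 35". The second is that the probability of lying in the 25% to 35% target interval is as large as possible. The definition of the MTD in the same section carries the same overdose condition.

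A note follows: "To fulfill the above statement, a loss function is being defined as per following". It sets four intervals (0 to 25%, 25 to 35%, 35 to 60%, 60 to 100%) with losses 1, 0, 1 and 2.

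Under "The dose-escalation will stop under the following circumstances" the section lists two cases. One is that 40 patients have been reached. The other needs at least 9 patients in 3 cohorts, at least 6 at the MTD, and a target-interval probability above 40%.

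The text below Figure 7 takes three patients treated at the 100 mg starting dose and gives the next step as follows: "when 1, 2, or 3 DLTs are observed, then the dose recommended for the second cohort is 100 mg, 50 mg, or 50 mg". The doses are listed in the order of the DLT counts. This case and nine further starting points are tabulated in Table 5, under the column heading "Recommended Dose among the Number of DLT Effectively Observed". The text after that table also puts a ceiling on what the next cohort may receive: "the highest allowable dose based on the pre-specified over-dose constraints, whichever is lower".

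The increment limits include "33% of relative increase if the last idasanutlin dose is above 300 mg". The six-patient illustration, said to respect these limits, reads "the sequence of cohorts is 100 mg, 250 mg, 300 mg, 300 mg, 350 mg, 400 mg, 600 mg".

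**The concern.** A loss function that weighs intervals is a different thing from a hard limit on the probability of overdosing. If the loss alone drives the recommendation, the overdose control in the design's name is not operating, and the printed examples would show it.

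This matters most after heavy early toxicity. If two or three of the first three patients have DLTs at the starting dose, the stated criterion may admit no dose while the worked example says to treat the next cohort at 50 mg. The sponsor and investigators would then hold two conflicting instructions. Section 3.1.2.3 also reuses a similar algorithm for the DLBCL and Regimen B bridging cohorts, so the gap carries forward. It also bears on whether the operating characteristics in Appendix 11 describe the design as written.

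**Working it through.** **Inputs (Section 3.1.2.3, Tables 4 and 5).** The model is logit p(d) = log α + β·log(d/300). The prior is log α ~ N(−1.237, variance 2.661) and log β ~ N(0.460, variance 1.816), uncorrelated. Doses run from 50 to 800 mg in 50 mg steps. Increment caps are 151% up to 300 mg and 33% above. Posteriors were computed by numerical integration on a grid, using Table 5's own dose history with earlier cohorts free of DLTs. The 750 mg row is not on the three-patient path in the text, so it was scored as following 600 mg. The six cells at issue come before it and are unaffected.

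**What the loss contains.** Expected loss = P(<25%) + P(35–60%) + 2·P(>60%) = 1 − P(25–35%) + P(>60%). The quantity P(>35%) does not appear as a limit.

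**Reproducing Table 5 (30 cells).**

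| Rule | Cells matched |
|---|---|
| Minimum loss, no overdose limit | 28 |
| Minimum loss among doses with P(>35%) < 0.35 | 22 |
| Maximum P(25–35%) among doses with P(>35%) < 0.35 | 14 |

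The two cells that neither loss version matches are 250 mg with 3 DLTs (100 printed, 150 computed) and 500 mg with 1 DLT (500 printed, 550 computed). The losses there are close: 0.910 against 0.896, and 0.921 against 0.918.

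**Where the limit changes the answer.** The two loss rules differ in exactly six cells, and Table 5 prints the value without the limit in all six.

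| DLTs observed | Printed dose | P(>35%) at that dose | Dose with limit applied |
|---|---|---|---|
| 2/3 at 100 mg | 50 mg | 0.47 (mean DLT rate 36%) | none |
| 3/3 at 100 mg | 50 mg | 0.82 (mean 58%; P(>60%) 0.50) | none |
| 3/3, second 300 mg cohort | 300 mg | 0.47–0.48 | 250 mg |
| 3/3 at 400 mg | 350 mg | 0.37 | 300 mg |
| 3/3 at 450 mg | 400 mg | 0.41 | 350 mg |
| 3/3 at 500 mg | 450 mg | 0.36 | 400 mg |

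The second 300 mg cohort shows the mechanism. At 300 mg the loss is 1 − 0.251 + 0.069 = 0.818; at 250 mg it is 1 − 0.163 + 0.003 = 0.840. The loss therefore keeps 300 mg, although P(>35%) is about 0.47 there and 0.106 at 250 mg.

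**No admissible dose.** Table 4 starts at 50 mg, so in the first two rows nothing passes the criterion. With six patients in the first cohort, the same happens after 3/6 DLTs (0.37 at 50 mg) and 4/6 (0.65). Three or six patients do not satisfy either stopping circumstance.

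**How often.** The chance of 2/3 or 3/3 DLTs at 100 mg is 3q²(1−q) + q³:
- q = 8% (Table 4): 0.0177 + 0.0005 = 1.8%
- q = 8% × 1.3 = 10.4% (Scenario 2): 3.0%
- q = 8% × 1.8 = 14.4% (Scenario 4): 5.6%

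**Appendix 11.** With 3-patient cohorts starting at 100 mg, 500 simulated trials should include about 500 × 0.018 = 9 such trials in Scenario 1 and 500 × 0.056 = 28 in Scenario 4. Appendix 11 Table 3 gives a minimum sample size of 9 in both. The simulations therefore appear to have kept dosing when no dose met the criterion.

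**Increment entry.** 600/400 = 1.50 against a cap of 1.33. The loss with the caps gives 500 mg at that step. P(>35%) at 600 mg is only 0.08, so this is a wrong entry and not an overdose under the model.

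**The case against.** - **The later cells are rare, and three are marginal.** This is right. The 300, 400, 450 and 500 mg cells need 3/3 DLTs after 9 to 21 consecutive patients without one. At Table 4 risks along Table 5's path their combined chance is about 0.39% (0.06% to 0.46% in Scenarios 2, 3, 4 and 6), and applying the limit moves each by one 50 mg step. The practical weight lies in the two 50 mg cells, of which the 0.82 case occurs in only 0.08³ = 0.05% of trials at the prior guess.
- **The text after Table 5 already caps the dose.** If its over-dose constraints include the 35% limit, actual dosing in the four later cells would already be corrected. Table 5 would still misstate the recommendation, and the two 50 mg cells would still have no answer.
- **Discretion protects patients.** The examples are called illustrative, clinical judgment overrides the model (3.1.2.3), the sponsor and investigators review each cohort (3.1.2.2), the IMC can recommend a hold (3.1.4), and the sponsor can terminate (4.6.3). These are real backstops. None settles whether the pre-specified rule says no dose or 50 mg.
- **The code is unknown.** This also stands. The loss misses 4 of 10 printed steps on the three-patient DLT-free path and 2 of 8 on the six-patient path. The two loss rules agree at every one of those steps, so they cannot show whether the limit was used.
- **Bridging cohorts.** They start at the Regimen A MTD and no prior is stated, so no size can be given there.

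**Conclusion.** The concern holds and should be fixed. The loss function does not contain the 35% limit it is said to fulfil. Six of the 30 Table 5 doses breach that limit: three clearly (0.47, 0.82 and 0.47–0.48) and three more narrowly (0.36 to 0.41). After 2/3 or 3/3 DLTs at the starting dose the stated criterion admits no dose, the example prescribes 50 mg, and no pre-specified rule resolves the conflict.

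The count of six rests on reading the prior matrix as variances, the usual meaning of a covariance matrix and the reading that fits Table 5 best. Read as standard deviations, it also gives six breaches, in a partly different set, with a poorer fit. Read as precisions, it fits poorly and gives one. That the loss lacks the limit follows from its weights and depends on none of these readings. Which code produced Table 5 and Appendix 11 cannot be established from the documents. The 400 to 600 mg step is a separate, isolated error.

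**What to change.** 1. Keep the loss function, but state in its note that doses are first filtered by the 35% overdose limit and the increment caps, and that the loss is minimised among those remaining.
2. Add a rule: if P(DLT rate > 35%) is 35% or more at 50 mg, stop escalation or hold enrollment for IMC review.
3. Say that the same filter and rule apply in the bridging cohorts.
4. Regenerate Table 5, the DLT-free sequences and Appendix 11 Tables 2 and 3 from that code, and correct the 400 to 600 mg entry.

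The cost is a re-run of existing simulations and edits to Section 3.1.2.3 and Appendix 11. Some trials would stop earlier or de-escalate one step further. With three-patient cohorts, the first-cohort stop or hold would trigger wrongly in about 1.8% of trials if the true risk at 100 mg is 8%.

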**Table 5 Hypothetical Trial Realization (Cohort Size=3)**

Observation of First DLT at	Recommended Dose among the Number of DLT Effectively Observed		
	1 DLT	2 DLTs	3 DLTs
100 mg	100 mg	50 mg	50 mg
250 mg	250 mg	200 mg	100 mg
300 mg	300 mg	250 mg	250 mg
300 mg	300 mg	300 mg	300 mg
350 mg	350 mg	300 mg	300 mg
400 mg	400 mg	350 mg	350 mg
450 mg	450 mg	400 mg	400 mg
500 mg	500 mg	450 mg	450 mg
600 mg	650 mg	550 mg	500 mg
750 mg	800 mg	650 mg	600 mg

DLT=dose-limiting toxicity.

After each cohort of patients completes dosing, the posterior distribution of the model parameters of the logistic regression model will be updated with the observed DLT occurrence data and, hence, an estimate of the next dose, or declaration of MTD, will be derived. In addition relevant demographic, adverse event, laboratory, dose administration, and PK (if available) data will be reviewed. Then, subject to clinical judgment, a new cohort of patients will be dosed at the next recommended estimate of the MTD or the highest allowable dose based on the pre-specified over-dose constraints, whichever is lower. The design will continue as described, assigning patients to the MTD as estimated from all of the DLT data cumulatively, until one of the predefined stopping criteria is satisfied or the predetermined sample size of DLT-evaluable patients is reached, whichever comes first. *The above described mCRM algorithm will be first used for predicting the MTD in the combined FL/DLBCL dose-escalation cohorts where idasanutlin is given in combination with obinutuzumab. A similar mCRM will be then employed to support dose escalation in the DLBCL bridging cohorts where idasanutlin is given in combination with rituximab and in the FL bridging cohorts in which idasanutlin is given in combination with obinutuzumab using Regimen B, if applicable.*

With the end of the mCRM phase, a tentative MTD estimate is defined. Moreover, the recommended dose will be defined by taking into consideration all available data gathered so far.

### **3.1.3 Expansion Phase (Part 2)**

The expansion phase is designed to further assess the safety and efficacy of obinutuzumab in combination with idasanutlin at the RP2D *with the selected regimen in patients with R/R FL and of rituximab in combination with idasanutlin at the RP2D in patients with R/R DLBCL*. Approximately 80 patients (40 patients with R/R FL and 40 patients with R/R DLBCL) will be enrolled during the expansion phase and treated as described below. *The start of the expansion phase may not happen simultaneously for the two indications.*

All patients will receive 6 cycles of induction treatment, administered in 28-day cycles, as outlined in [Table 6](#). Patients with FL who achieve a CR or PR at the EOI will receive maintenance treatment with obinutuzumab and idasanutlin. *Patients with DLBCL who achieve a CR or PR at the EOI will receive consolidation treatment with rituximab and idasanutlin. Post-induction treatment should start 8 weeks ( $\pm 1$  week) after Day 1 of the final cycle of induction and will continue until disease progression or unacceptable toxicity for up to 2 years for maintenance treatment and 6 months for consolidation treatment (see [Table 7](#)).*

*Patients with DLBCL who achieve a CR based on modified Lugano 2014 criteria at the end of induction (defined as within 6-8 weeks after the start of the last cycle of study treatment) are allowed to proceed to hematopoietic stem cell transplantation if deemed appropriate by the investigator. Such patients will be followed for disease progression and survival.*

The schedules of assessments are provided in [Appendix 1](#) and [Appendix 2](#), and a study schema is provided in [Figure 6](#).

**Table 6 Induction Treatment for the Expansion Phase**

Induction Treatment (28-Day Cycles)		
Patients with FL	Regimen A a Obinutuzumab plus idasanutlin from Cycles 1•6	Regimen B a Obinutuzumab at Cycle 1 and obinutuzumab plus idasanutlin from Cycles 2•6
Cycle 1	
 
• Obinutuzumab 1000 mg IV on Days 1, 8, and 15
 
• Idasanutlin, oral, Days 1•5, RP2D in combination with obinutuzumab a
 
	
 
• Obinutuzumab 1000 mg IV on Days 1, 8, and 15
 

Cycles 2•6	
 
• Obinutuzumab 1000 mg IV on Day 1
 
• Idasanutlin, oral, Days 1•5, RP2D in combination with obinutuzumab
 
	
 
• Obinutuzumab 1000 mg IV on Day 1
 
• Idasanutlin, oral, Days 1•5, RP2D in combination with obinutuzumab
 

Patients with DLBCL		
Cycles 1•6	
 
• Rituximab 375 mg/m^2 IV on Day 1
 
• Idasanutlin, oral, Days 1•5, RP2D in combination with rituximab
 
	

DLBCL = diffuse large B-cell lymphoma; FL = follicular lymphoma; IV = intravenous; RP2D = recommended Phase II dose.

a The treatment regimen will be determined at the end of the dose-escalation phase.

**Table 7 Post-Induction Treatment for the Expansion Phase**

Post-Induction Treatment	
Patients with FL	Maintenance treatment consisting of the following: 
 
• Obinutuzumab 1000 mg IV every 2 months for 24 months
 
• Idasanutlin for 6 months a
 

Patients with DLBCL	Consolidation treatment consisting of the following: 
 
• Rituximab 375 mg/m^2 IV every 2 months for 6 months
 
• Idasanutlin for 6 months a
 

DLBCL = diffuse large B-cell lymphoma; FL = follicular lymphoma; IV = intravenous.

a Dose and regimen to be determined by the Sponsor after review of all relevant data. The dose for maintenance/consolidation will not exceed the dose the patient received during induction.

### **3.1.4 Internal Monitoring Committee**

An IMC will monitor patient safety throughout the study. The IMC will include Roche representatives from Clinical Science, Drug Safety, Biostatistics, and Statistical Programming and Analysis. In addition to the ongoing assessment of the incidence and nature of adverse events (particularly, Grade • 3 events), serious adverse events, deaths,

and laboratory abnormalities performed by the investigator and the Medical Monitor, the IMC will review all necessary cumulative data at regular intervals during the study. At the time of each review, the IMC will make appropriate recommendations (e.g., the study should continue as planned, additional analyses should be performed, enrollment should be held pending further safety evaluations). Decisions will be made in consideration of the totality of the available data. Ad hoc meetings may be called in addition to scheduled meetings, as necessary, to provide recommendations on management of any potential new safety signals. Specific operational details, such as the committee's composition, frequency and timing of meetings, members' roles and responsibilities, and data to be reviewed, will be detailed in an IMC Charter.

